Abbreviation: PC, phone contact; V, clinic visit; T, telephone call; AE, adverse event; SAE, serious adverse event; AESI, adverse events of special interest. Note: All procedures to be performed prior to study intervention administration (as applicable). The study timepoints are the same for all groups, irrespective of the staggered enrolment (See Section 8.2.2.1).

* Diagnosis of coronavirus 2019 (COVID-19) should be made in accordance with the World Health Organization case definitions. Cases should be reported as AEs or SAEs (refer to Section 10.3 for the definitions), and routine procedures for recording, evaluation, follow-up, and reporting of AEs, and SAEs should be followed in accordance with the protocol-defined time periods (refer to Table 34). In addition, separate COVID-19 specific eCRF form(s) should be completed

Note: Refer to Section 8 for information on study procedures during special circumstances

Table 2 Intervals between study visits/contacts –Phase I

Interval	Planned visit/ phone call interval	Allowed interval range (visit window)
Visit V1 → Visit V2	7 days	6 to 8 days (-1 to +1 days)
Visit V1 → Visit V3	30 days	44 days (+14 days)
Visit V3 → Telephone contact T1	7 days	6 to 8 days (-1 to +1 days)
Visit V3 → Visit V4	30 days	25 to 44 days (-5 to +14 days)
Visit V3 → Telephone contact T2	120 days	113 to 134 days (-7 to +14 days)
Visit V3 → Telephone contact T3	180 days	173 to 194 days (-7 to +14 days)

Table 3 Schedule of activities – Phase II (Formulation and schedule-finding)

Type of contact	Visit	PC	Visit	PC	Visit	PC	Visit	Visit	PC	PC	PC	Visit	Notes
Visit/Phone call no.	V1	T1	V2	T2	V3†	TC††	V4	V5	T3	T4	T5	V6	
Timepoint(s) [refer to Table 4 for visit windows]	Day 1	Day 8	Day 31	Day 91	Day 121	Day 121	Day 181	Day 211	Day 271	Day 361	Day 451	Day 541	
Groups	All	First 45**	All	All	ABCWY groups	Control group	All	All	All	All	All	All	
Informed consent	●												Confirm consent form signed prior to any procedures. Before performing any study-related activities, check the randomisation system to ensure that enrolment is still open See Section 10.1.3 for details
Informed assent, if applicable	○												Confirm assent form (if applicable) signed prior to any procedures

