3. OBJECTIVES AND ENDPOINTS

Table 11 Study objective(s) and endpoints

(Amended 22 March 2022)

Objectives	Endpoints
Phase I – Safety lead-in, Dose escalation	
Primary	
To evaluate the safety and reactogenicity of the 2 formulations (CCI) of the CCI vaccine.	
 The frequencies and percentages of participants with solicited administration site and systemic events during the 7 days (including the day of vaccination) following each vaccination at Day 1 and Day 31 in all groups. The frequencies and percentages of participants with any unsolicited AEs (including all SAEs, AEs leading to withdrawal, and AESIs) during the 30 days (including the day of vaccination) following each vaccination at Day 1 and Day 31 in all groups. The frequencies and percentages of participants with SAEs, AEs leading to withdrawal and AESIs throughout the study period in all groups (Day 1 through Day 211). The frequencies and percentages of participants with haematological and biochemical laboratory abnormalities, and changes from the baseline values, after the first vaccination at Day 8, in all groups.
Phase II – Formulation and Schedule-finding	
Primary	
To demonstrate the superiority of the effectiveness of the CCI vaccine (CCI) when administered at 0,2- or 0,6-months schedule, compared to the MenB vaccine administered at 0,6-months schedule*.	The percentages of samples with bactericidal serum activity using enc-hSBA against a panel of 110 randomly selected endemic US N. meningitidis serogroup B invasive disease strains at 1 month after the last vaccination (Day 211, Month 7) in all groups.
To demonstrate the immunological non-inferiority of the CCI vaccine (CCI) administered at 0,2- or 0,6-months schedule compared to the MenACWY vaccine (single dose)*;†.	
The percentages of participants achieving a 4-fold rise** in hSBA titres against serogroups A, C, W and Y at 1 month after the
 
 last CCI vaccination (Day 211, Month 7) for the ABCWY groups and, MenACWY vaccination (Day 31, Month 1) in the Control group, 
relative to Day 1, Month 0 in C, C and Control groups and relative to 3 months pre-first CCI vaccination (Day 31, Month 1) in C groups.

CONFIDENTIAL

212458 (MENACWY=CCI -001 PRI)

Protocol Amendment 4 Final

Objectives	Endpoints

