8.1.1. Biological samples

8.1.1.1. Blood sample

(Amended 22 March 2022)

Phase I: An overall blood volume of approximately 240 mL per participant will be collected over the course of the Phase I part of the study. An additional 7 mL of blood will be collected at Visit V1 and Visit V2 from all participants for the safety laboratory evaluation. Refer to [Table 24](#) for details.

Table 24 Blood samples at Phase I

Sample type	Quantity	Unit	Timepoint	Subset name/ Group	Day
Blood	Approximately 80	mL	Visit V1 (CCI [REDACTED]);	All participants	Day 1
Blood	Approximately 80	mL	Visit V3 (CCI [REDACTED]);	All participants	Day 31
Blood	Approximately 80	mL	Visit V4 (CCI [REDACTED])	All participants	Day 61
Blood	Approximately 7	mL	Visit V1	All participants	Day 1
Blood	Approximately 7	mL	Visit V2	All participants	Day 8

Pre-Vacc, Pre-vaccination timepoint; Post-Vacc, Post-vaccination timepoint

Refer to [Table 1](#) (SoA for Phase I) for details of visits.

Phase II (sourcing): An overall blood volume of approximately 285 mL per participant will be collected over the course of the Phase II, Sourcing part of the study. Please refer to [Table 25](#) and [Table 26](#) for details.

Table 25 Blood samples at Phase II (Sourcing; 0,1 month vaccination schedule)

Sample type	Quantity	Unit	Timepoint	Subset name/ Group	Day
Blood	Approximately 95	mL	Visit V1 (CCI [REDACTED]);	All participants	Day 1
Blood	Approximately 95	mL	Visit V2 (CCI [REDACTED])	All participants	Day 31
Blood	Approximately 95	mL	Visit V3 (CCI [REDACTED])	All participants	Day 61

Pre-Vacc, Pre-vaccination timepoint; Post-Vacc, Post-vaccination timepoint

Refer to [Table 5](#) (SoA for Phase II, Sourcing) for details of visits.

Table 26 Blood samples at Phase II (Sourcing; 0,2 and 0,6 month vaccination schedule)

Sample type	Quantity	Unit	Timepoint	Subset name/ Group	Day
Blood	Approximately 95	mL	Visit V1 (CCI [REDACTED]);	All participants	Day 1
Blood	Approximately 95	mL	Visit V3 (CCI [REDACTED]);		Day 76
					Day 196
					Day 91
Blood	Approximately 95	mL	Visit V4 (CCI [REDACTED])		Day 211

Pre-Vacc, Pre-vaccination timepoint; Post-Vacc, Post-vaccination timepoint.

Refer to [Table 6](#) and [Table 7](#) (SoA for Phase II, Sourcing) for details of visits.

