8.2.2.1. Safety data review

8.2.2.1.1. Safety evaluation

For Phase I of the study, a staggered enrolment of healthy volunteers will be performed, as described in Figure 4.

Figure 4 Step-wise approach for safety review in Phase I (Safety Lead-in)

Abbreviation: N, number of participants; V, clinic visit; D, day; iSRC, internal safety review committee; PC, phone contact; BS, blood sample.

Note: This is a simplified study design aimed to show the safety review in Phase I. To see the detailed study design, refer to Figure 1

[figure not shown]
An iSRC, composed of senior GSK experts independent from the study team, will meet at pre-defined timepoints to perform safety monitoring through unblinded review of safety data.

The following step-wise approach will be followed for the safety evaluation during the Phase I Safety Lead-in:

- Step 1: Following the first vaccination in [REDACTED] (12 participants) and [REDACTED] (4 participants) groups, all available safety data from all participants collected up to Day 8 will be evaluated by the iSRC. The iSRC will be responsible for making the first “go-no go” decision based on unblinded data. If a “go” decision is made, the enrolment in groups [REDACTED] will start and the administration of the second vaccination will take place in groups [REDACTED].
- Step 2: Following the first vaccination in [REDACTED] (12 participants) and [REDACTED] (4 participants) groups, all available safety data from all participants collected up to Day 8 will be evaluated by the iSRC. The iSRC will be responsible for making the second “go-no go” decision based on unblinded data. If a “go” decision is made, the administration of the second vaccination will take place for participants in groups [REDACTED].
- Step 3: Following the second vaccination in [REDACTED] groups at Day 31, all available safety data from all participants collected up to Day 38 will be evaluated by the iSRC. The iSRC will be responsible for making the third “go-no go” decision based on unblinded data. If a “go” decision is made, the Phase II enrolment will start parallelly for the 2 parts: Phase II (sourcing) and Phase II (formulation and schedule-finding).

For Phase II, Formulation and Schedule-finding part of the study, a staggered enrolment of healthy volunteers will be performed, as described in [Figure 5](#), for the iSRC safety evaluation of the first 45 enrolled participants (Phase II safety lead-in).

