These holding rules have been written under the assumption that the safety data from all participants will be available. If the data from all participants are not available (i.e. in case a participant is lost to follow-up), then the holding rules will be assessed on a pro-rata basis.

Of note, no formal holding rules will be applied for other safety data such as missed visits due to study intervention related AEs, Grade 1 and Grade 2 solicited and unsolicited AEs in the 7-day follow-up period and unsolicited AEs collected from Day 8 to Day 30 after study intervention administration. However, if available, these data will also be reviewed by the iSRC to allow an overall assessment of the benefit/risk ratio of study intervention administration.

The iSRC can also meet ad-hoc during the entire safety lead-in phase (Phase I).

Table 32 Study holding rules – Phase I

Holding rule	Event	Number or % of participants needed to trigger the hold
1a	Death or any life-threatening SAE regardless of causality	≥ 1
1b	Any non-life-threatening SAE that can be reasonably attributed to the vaccination	≥ 1
1c	Any withdrawal from the study (by investigator or participant request) following a Grade 3 AE that can be reasonably attributed to the vaccination.	≥ 1
1d	Fever >40°C (104°F) OR any solicited administration site and/or systemic events leading to hospitalisation , OR necrosis at the injection site, each with an event onset within the 7-day (Day 1-7) post-vaccination period	≥ 1
2a	Any Grade 3 solicited administration site event (lasting 48h or more) in the investigational group, with an event onset within the 7-day (Day 1-7) post-vaccination period	≥ 20%
2b	Any Grade 3 solicited systemic event (lasting 48h or more) in an investigational group, with an event onset within the 7-day (Day 1-7) post-injection period	≥ 20%
2c	Any Grade 3 unsolicited AE in an investigational group, that can be reasonably attributed to the vaccination, with an event onset within the 7-day (Day 1-7) post-injection period OR Any Grade 3 abnormality in pre-specified haematological or biochemical laboratory parameters* in an investigational group with an event onset within the 7-day (Day 1-7) post-vaccination period	≥ 20%

Abbreviations: AE, adverse event; SAE, serious adverse event.

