10.3.10.2. Back up system in case the electronic reporting system does not work

If the electronic reporting system does not work, the investigator (or designee) must fax a completed, dated and signed paper Expedited AEs Report to the study contact for reporting SAEs (refer to the [SPONSOR INFORMATION](#)) or to GSK VCSP department within 24 hours of becoming aware of the SAE.

Investigator (or designee) must complete the electronic Expedited AEs Report within 24 hours after the electronic reporting system is working again. The information reported through the electronic SAE reporting system will be considered valid for regulatory reporting purposes.

10.4. Appendix 4: FDA's toxicity grading scale for healthy adult and adolescent volunteers enrolled in preventive vaccine clinical trials applied for this study

The laboratory values provided in the tables below serve as guidelines and are dependent upon institutional normal parameters. Institutional normal reference ranges should be provided to demonstrate that they are appropriate.

Table 49 Laboratory abnormalities

	Mild (Grade 1)	Moderate (Grade 2)	Severe (Grade 3)	Potentially life-threatening (Grade 4)**
Serum*				
Creatinine – mg/dL	1.5 – 1.7	1.8 – 2.0	2.1 – 2.5	>2.5 or requires dialysis
Liver function tests – ALT, AST increase by factor	1.1 – 2.5 x ULN***	2.6 – 5.0 x ULN	5.1 – 10 x ULN	>10 x ULN
Haematology*				
Haemoglobin (Female) - gm/dL	11.0 – 12.0	9.5 – 10.9	8.0 – 9.4	< 8.0
Haemoglobin (Female) change from baseline value - gm/dL	Any decrease – 1.5	1.6 – 2.0	2.1 – 5.0	> 5.0
Haemoglobin (Male) - gm/dL	12.5 – 13.5	10.5 – 12.4	8.5 – 10.4	< 8.5
Haemoglobin (Male) change from baseline value – gm/dL	Any decrease – 1.5	1.6 – 2.0	2.1 – 5.0	> 5.0
WBC Increase - cell/mm ³	10,800 – 15,000	15,001 – 20,000	20,001 – 25,000	> 25,000
WBC Decrease - cell/mm ³	2,500 – 3,500	1,500 – 2,499	1,000 – 1,499	< 1,000
Lymphocytes Decrease - cell/mm ³	750 – 1,000	500 – 749	250 – 499	< 250
Neutrophils Decrease - cell/mm ³	1,500 – 2,000	1,000 – 1,499	500 – 999	< 500
Eosinophils - cell/mm ³	650 – 1500	1501 – 5000	> 5000	Hypereosinophilic
Platelets Decreased - cell/mm ³	125,000 – 140,000	100,000 – 124,000	25,000 – 99,000	< 25,000

* The laboratory values provided in the tables serve as guidelines and are dependent upon institutional normal parameters. Institutional normal reference ranges should be provided to demonstrate that they are appropriate.

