10.1.3.11. Onset day

The onset day for an event (e.g., AE, concomitant medication/vaccination) is the number of days between the last study dose and the start date of the event. This is 1 for an event occurring on the same day as a study dose (and reported as starting after study dose).

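### Does the laboratory limb of Phase I holding rule 2c miss the planned Day 8 safety sample and Grade 4 values?

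*Protocol*

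**What the plan says.** Table 32 in Protocol Section 8.2.2.1.3 sets the Phase I holding rules. The laboratory limb of rule 2c reads: "Any Grade 3 abnormality in pre-specified haematological or biochemical laboratory parameters* in an investigational group with an event onset within the 7-day (Day 1-7"). Its threshold is 20% or more of participants, and its footnote points to the toxicity scale in Section 10.4. Table 49 there has four grades, with potentially life-threatening values as a separate Grade 4 column.

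On sampling, Section 8.1.1.1 says "An additional 7 mL of blood will be collected at Visit V1 and Visit V2 from all participants for the safety laboratory evaluation". Table 1 puts V1 on Day 1, with the draw before vaccination, and V2 on Day 8. Table 2 plans V2 at 7 days after V1 and allows one day either side. The Phase I laboratory endpoint in Table 11 is likewise "after the first vaccination at Day 8, in all groups".

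On review, Steps 1 and 2 of Section 8.2.2.1.1 state that "all available safety data from all participants collected up to Day 8 will be evaluated by the iSRC". The same section lists Phase I laboratory data among the unblinded data the committee receives.

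The protocol does not say how the onset of a laboratory abnormality is dated. SAP Section 10.1.3.11 defines onset day for events in general: it "is the number of days between the last study dose and the start date of the event", and is 1 on the dosing day.

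**The concern.** Two things in rule 2c do not line up with the rest of the protocol.

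The first is the window. If a laboratory abnormality is dated by the day the blood was taken, a result from the planned V2 draw falls one day after the window closes. Section 8.2.2.1.3 lends this reading some support, because it lists "unsolicited AEs collected from Day 8 to Day 30 after study intervention administration" among the data to which no formal holding rule applies.

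The second is the grade. The rule names Grade 3 alone, while the scale it cites goes one step higher, so the worst values would not count.

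At stake is a numerical trigger for escalation in a first-in-human, dose-escalating part. Two readers could count the same data and disagree on whether the trigger was met.

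**Working it through.** **1. Study days.** The vaccination day is Day 1 (Protocol Section 10.3.8.1; SAP Section 10.1.3.11), so study day = 1 + days since V1. The planned interval gives 1 + 7 = 8, which reproduces the plan's Day 8.

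| Days after V1 | Study day of V2 | Inside Day 1-7? |
|---|---|---|
| 6 (earliest allowed) | 7 | yes |
| 7 (planned) | 8 | no |
| 8 (latest allowed) | 9 | no |

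Under draw-dating, 0 of 12 on-schedule results per group can count. If onset may precede the draw, up to 12 of 12 can.

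**2. Threshold.** Section 9.2.1 gives 12 per investigational group. 0.20 × 12 = 2.4, so three participants are needed: 3/12 = 25.0% meets the rule and 2/12 = 16.7% does not. The pro-rata clause in Section 8.2.2.1.3 can lower the count: with 10 evaluable participants, 2/10 = 20% is enough.

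**3. Grade.** Take two Grade 3 values and one Grade 4 value among 12. Literally this is 2/12 = 16.7%, not met. With the Grade 4 value counted it is 3/12 = 25.0%, met.

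**4. How far the reading could move the numerical trigger.** The documents give no event rate, so the rates below are assumptions. P(trigger) = 1 − Σ(k = 0 to 2) C(12,k) q^k (1−q)^(12−k), where q is the countable rate. With p the true rate of Grade 3 or worse values, q = p if everything counts, 0.75p if a quarter of those values are Grade 4 and left out, and p/3 if a third of draws fall on Day 7 and only those count.

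| Assumed p | All counted | Quarter are Grade 4, not counted | Only Day 7 draws count (one third) | No Day 7 draws, draw-dated |
|---|---|---|---|---|
| 20% | 0.44 | 0.26 | 0.04 | 0 |
| 30% | 0.75 | 0.53 | 0.11 | 0 |
| 40% | 0.92 | 0.75 | 0.21 | 0 |
| 50% | 0.98 | 0.89 | 0.32 | 0 |

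The reading matters a good deal to the count.

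**5. What depends on the count.** Section 8.2.2.1.2 imposes one duty in either of two cases: a safety signal is seen during the evaluation, or one of rules 2a to 2c is met. In both, the committee chair must urgently communicate within the sponsor and give the rationale for holding or not holding. Section 8.2.2.1.3 adds that medical judgement on all available safety data is the basis for continuing. A cluster of severe Day 8 values is in front of the committee unblinded and can reach that duty without rule 2c.

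**6. Where the rule still applies.** Section 4.1.2 and Step 3 of Section 8.2.2.1.1 open Phase II only after the last Phase I review. Section 9.2.3 reports 107 Phase II (Sourcing) participants already enrolled. Safety laboratory tests are done in Phase I only (Sections 8.2.2.1.1 and 10.2.1), and rule 2c in Table 33, for Phase II, has no laboratory limb.

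**7. Reported results.** The Phase I laboratory endpoint is defined at Day 8 and does not use the rule's onset window, so the stated endpoint does not depend on how rule 2c is read.

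**The case for a change.** The best argument for a change is that a stated numerical trigger in first-in-human escalation should match its only scheduled post-dose sample and its own grading scale, and that a duty to escalate should not depend on who reads the rule. The other routes are not automatic substitutes. Rule 1a needs a life-threatening SAE, and Section 10.3.2 limits that to actual risk of death, so a Grade 4 value does not qualify by itself. The adverse-event limb of 2c has the same Day 1-7 window and also needs attribution to vaccination. Section 8.3.2.1 requires repeat tests only for clinically significant values, and repeats of V2 results come later still.

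All of that is correct, and the ambiguity in the count stands. Three things limit it.

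- **The draw-date reading is not the protocol's own.** Rule 2c speaks of onset. The SAP rule uses the start of the event, not its detection, and the Day 8 to Day 30 sentence concerns unsolicited AEs. V2 is the only scheduled sample the limb can be about, so a committee would have little reason to adopt a reading that leaves the limb almost empty.
- **The grade wording looks carried over.** The intensity scales for solicited and unsolicited events (Section 10.3.9.1) stop at 3, so in rules 2a, 2b and the adverse-event limb Grade 3 is the top category. Section 8.2.2.1.3 lists Grade 1 and Grade 2 events as outside the formal rules, and nothing above Grade 3. That suggests loose drafting more than an intended exclusion.
- **The escalation duty does not rest on the count alone**, as step 5 shows.

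**Conclusion.** No change to the plan follows. The laboratory limb of rule 2c does not agree with Tables 1, 2 and 24 on the sampling day or with Table 49 on grades, and onset of a laboratory value is undefined. These passages must be reconciled by the sponsor; I take no view on what the rule should be. The effect is confined to the numerical count: between 0 and 12 of 12 on-schedule results per group can count, depending on the reading, against a threshold of 3. The data reviewed, the basis for the decision and the duty to escalate on a safety signal are the same under either reading, and no later review uses the limb.

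This rests on two points. Completion of the Phase I reviews is inferred from Phase II (Sourcing) enrolment, not stated. The iSRC charter and review records are not among the documents, so they may already say how Day 8 and any Grade 4 values were counted. If they do not, a sentence in the study report would be good housekeeping. Were the Phase I reviews still ahead, the wording would be worth settling before the first one.

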8.3. Adverse Events (AEs), Serious Adverse Events (SAEs) and other safety reporting

8.3.1. Time period and frequency for collecting AE, SAE and other safety information

(Amended 22 March 2022)

An overview of the protocol-required reporting periods for AEs, SAEs, AESIs and pregnancies is given in [Table 34](#) for Phase I and [Table 35](#) for Phase II. Refer to the Section [10.3.8.1](#) for details on the time period for recording safety information.

Table 34 Timeframes for collecting and reporting of safety information – Phase I

Event	On V1*	V1 D1***	V3 D7	V4 D31	PC D37	D61	Phase I conclusion D 211 (PC)
Solicited administration site and systemic events							
Unsolicited AEs**							
AEs leading to withdrawal from the study**							
SAEs**							

CONFIDENTIAL

212458 (MENACWY=CCI -001 PRI)

Protocol Amendment 4 Final

Event	On V1*	V1 D1***	V3 D7	V4 D31 D37 D61	PC D151	Phase I conclusion D 211 (PC)
SAEs related to study participation or concurrent GSK medication/vaccine						
AESIs**						
Pregnancies**						

* i.e. consent obtained.; V: Visit; D: Day, M: Month; PC=Phone call

** Including COVID-19 infection-related AEs; Recording of unsolicited AEs is only from Day 1 to Day 30 post-vaccination

*** Except SAEs related to study participation or concurrent GSK medication/vaccine, all other safety data will be collected starting from Visit 1 after vaccine administration

Table 35 Timeframes for collecting and reporting of safety information – Phase II (Formulation and schedule-finding)

Event	On V1*	V1 D1***	V2 D7	V3# D121 D127 D151			V4 D181	V5 D 187	PC D 211	V6 Study Conclusion D541 D361
Solicited administration site and systemic events										
Unsolicited AEs**										
AEs leading to withdrawal from the study**										
SAEs**										
SAEs related to study participation or concurrent GSK medication/vaccine										
AESIs**										
Pregnancies**										

* i.e. consent obtained.; V: Visit; D: Day, M: Month; PC = Phone call

#Solicited AEs and unsolicited AEs will be collected only for [REDACTED] groups at Visit V3 (Control group will have a phone call at this time point (TC) where other safety follow-up will be done)

** Including COVID-19 infection-related AEs; Recording of unsolicited AEs is only from Day 1 to Day 30 post-vaccination

*** Except SAEs related to study participation or concurrent GSK medication/vaccine, all other safety data will be collected starting from Visit 1 after vaccine administration

**Table 36 Timeframes for collecting and reporting of safety information – Phase II
(Sourcing; 0,1 month vaccination schedule)**

Event	On V1*	V1		V2		V3		PC Day 151	Study conclusion D 211 (PC)
		D1***	D7	D31	D37	D61			
Solicited administration site and systemic events									
Unsolicited AEs**									
AEs leading to withdrawal from the study**									
SAEs**									
SAEs related to study participation or concurrent GSK medication/vaccine									
AESIs**									
Pregnancies**									

* i.e. consent obtained.; V: Visit; D: Day, M: Month; PC=Phone call

** Including COVID-19 infection-related AEs; Recording of unsolicited AEs is only from Day 1 to Day 30 post-vaccination)

*** Except SAEs related to study participation or concurrent GSK medication/vaccine, all other safety data will be collected starting from Visit 1 after vaccine administration

Table 37 Timeframes for collecting and reporting of safety information – Phase II (Sourcing; 0,2 month vaccination schedule)

Event	On V1*	V1	PC	V2	V3	V4	PC	Study conclusion D 241 (PC)
		D1***	D7	D31	D61	D67	D76	
Solicited administration site and systemic events								
Unsolicited AEs**								
AEs leading to withdrawal from the study**								
SAEs**								
SAEs related to study participation or concurrent GSK medication/vaccine								
AESIs**								
Pregnancies**								

* i.e. consent obtained.; V: Visit; D: Day, M: Month; PC=Phone call

** Including COVID-19 infection-related AEs; Recording of unsolicited AEs is only from Day 1 to Day 30 post-vaccination)

*** Except SAEs related to study participation or concurrent GSK medication/vaccine, all other safety data will be collected starting from Visit 1 after vaccine administration

Table 38 Timeframes for collecting and reporting of safety information – Phase II (Sourcing; 0,6 month vaccination schedule)

Event	On V1*	V1	PC	V2	V3	V4	PC	Study conclusion	
		D1***	D7	D31	D181	D187	D196	D211	Day 301
Solicited administration site and systemic events									
Unsolicited AEs**									
AEs leading to withdrawal from the study**									
SAEs**									
SAEs related to study participation or concurrent GSK medication/vaccine									
AESIs**									
Pregnancies**									

* i.e. consent obtained.; V: Visit; D: Day, M: Month; PC=Phone call

** Including COVID-19 infection-related AEs; Recording of unsolicited AEs is only from Day 1 to Day 30 post-vaccination)

*** Except SAEs related to study participation or concurrent GSK medication/vaccine, all other safety data will be collected starting from Visit 1 after vaccine administration

The investigator or designee will record and immediately report all SAEs to the sponsor via the Expedited AE Reporting Form. Reporting should, under no circumstances, occur later than 24 hours after the investigator becomes aware of an SAE, as indicated in Section 10.3.10. The investigator will submit any updated SAE data to the sponsor within 24 hours of it being available.

A post-study AE/SAE is defined as any event that occurs outside of the AE/SAE reporting periods defined in Table 34. Investigators are not obligated to actively seek AEs or SAEs from former study participants. However, if the investigator learns of any SAE, including a death, at any time after a participant has been discharged from the study, and he/she considers the event to be reasonably related to the study intervention, the

investigator will promptly notify the study contact for reporting SAEs mentioned in the [Table 40](#).

